5.8 PATIENT REGISTRATION

After ensuring that the patient meets all eligibility criteria and has given written informed consent, he/she can be registered in the study by means of the Interactive Voice Response System (IVRS, ICOPhoneTM). Authorized site staff will be provided with a personal user ID and PIN Code to access the system. To start the randomization process, the site responsible should dial the country-specific phone number supplied in the IVRS Manual (given as a separate document). The system will require the following information to be provided: patient number (six digits: four digits for site code, preassigned, plus two numbers assigned consecutively for every site's patients), date of birth, ECOG-PS score, Durie-Salmon stage at first diagnosis and planned treatment date (the planned treatment date must be seven days or less from the Randomization date). A confirmation report will be sent via e-mail once the randomization call will end, listing the above information plus the treatment arm the patient has been assigned to. The aforementioned patient number should be used on all future documentation and correspondence referring this patient.

A patient who has been treated prior to registration will not be accepted for the study at a later date.

5.9 PATIENT ASSIGNMENT TO TREATMENT GROUP

See Section 5.10 Patient Randomization.

5.10 PATIENT RANDOMIZATION

Eligible patients will be stratified according to their ECOG-PS score (0 and 1 vs. 2) and Durie-Salmon stage (I/II vs. III) and then randomized using a 2:1 randomization procedure to Arm A (plitidepsin in combination with dexamethasone) or Arm B (dexamethasone alone). Randomization will be used to avoid bias in the assignment of subjects to treatment, and to increase the likelihood that known and unknown subject attributes (e.g., demographics and baseline characteristics) are evenly balanced across treatment groups.

Randomization of patients should occur as close in time as possible before administration of the first dose of study drug(s) and must occur within 7 days of the patient receiving the first dose of study treatment. Patients will be assigned to each

group by strata random lists, so that a patient will have a two-thirds chance of getting Arm A (plitidepsin in combination with dexamethasone) and a one-third chance of getting Arm B (dexamethasone alone). The random permuted blocks method will be used; the size of the blocks in the randomization list will be fixed and not accessible to the investigators. To select the blocks, a uniform (0, 1) variable with a random seed will be used.

5.11 EVALUATION DURING TREATMENT

TREATMENT	INVESTIGATIONS	ТІМЕ
Clinical examination	Physical exam including weight, height and BSA.	On D1 of each cycle before study drug administration.
	PS (ECOG), vital signs (heart rate, BP, body temperature).	On D1 and D15 of every cycle before study drug administration.
	Concomitant treatments.	Throughout the study.
Hematology	Differential WBC, hemoglobin, hematocrit and platelets.	On D1 and D15 of every cycle before study drug administration, with a window of -2 days. If CTCAE grade \geq 3 occurs, the hematological counts should be assessed at least every 2-3 days in the case of grade 4 non-febrile neutropenia and everyday in case of grade 4 febrile neutropenia.
Biochemistry	Biochemistry A: AST, ALT, total bilirubin, direct bilirubin (in case total bilirubin is above ULN), AP, creatinine (calculated creatinine clearance by Cockcroft and Gault's formula; see Appendix 3), glucose, serum electrolytes (Na ⁺ , K ⁺ , Mg ⁺⁺ , Ca ⁺⁺), CPK, (CPK-MB fraction should be measured only if CPK is abnormally high) and troponin I*.	On D1 and D15 of every cycle before study drug administration, with a window of -2 days. If CTCAE grade \geq 3 occurs, the abnormal test(s) should be assessed at least every 2-3 days until recovery.
	Biochemistry B: Uric acid, LDH, total proteins, albumin. Coagulation tests : PT, PTT and INR.	On D1 of every cycle, except on D1 of Cycle 1, and with a window of -5 days.
Pregnancy test	Serum HCG	Repeat if applicable; always prior to study drug administration.
Adverse Events		Throughout the study.
Cardiac assessment	ECG: It should allow rhythm definition (at least 30 seconds of duration). Troponin I*.	Before each study drug administration, symmetrically in both arms. After the first two cycles, ECG will be done only on D1 of each cycle.
	LVEF assessment by ECHO or MUGA.	Every 12 weeks, with a window of \pm 2 weeks. When due, LVEF will be performed within 7 days of plitidepsin administration, except in non- primarily cardiac origin acutely ill

 Table 4. Evaluation during treatment

TREATMENT	INVESTIGATIONS	TIME
		hospitalized patients, until resolution.
Pharmacokinetics	Plitidepsin PK will be evaluated in at least 100 patients receiving both plitidepsin and dexamethasone (Arm A).	A total of 13 blood samples will be collected during the first three infusions [infusions 1 and 2 of Cycle 1 (Days 1 and 15), and infusion 1 of cycle 2 (Day 1)] using a sparse sampling schedule (see details in Table 5)
Central Lab Serum protein	Patients with secretory MM will be followed with serum electrophoresis, immunoglobulins quantification and M protein quantification in the Central Lab starting on Day 1 of Cycle 1; patients with oligo or non-secretory MM, will be followed with sFLC ratio, in case it has been abnormal at study entry; in case of M protein disappearance, immunofixation will be done to confirm CR, and if CR is confirmed, sFLC ratio will be performed, to determine sCR.	All protein assays will be done symmetrically every four weeks (i.e., Day 1 of every 4-week cycle, with a window of \pm 2 days) in both treatment arms, irrespectively of treatment delays or omissions.
Central Lab Urine protein	Only if Bence-Jones proteinuria is present at entering the study, in the Central Lab starting on Day 1 of Cycle 1.	Every four weeks (with a window of \pm 2 days) symmetrically in both treatment arms, irrespectively of treatment delays or omissions.
Serum β-2 microglobulin		Every 8 weeks (with a window of ±2 days).
Bone marrow Radiological	In all patients while in treatment, BM evaluation is mandatory at screening and in case of CR (including flow cytometry or immunohistochemistry, to demonstrate the presence of clonal plasma cells, only in those patients with presumed CR). In patients with non-secretory MM it must be repeated 6 weeks later to confirm response or as clinically indicated.	When serum protein indicates CR.
tumor assessment only in case of measurable soft tissue plasmacytoma		weeks) or if response is observed or if clinically indicated.
Skeletal evaluation	May be done using CT-scan or X-ray, provided the same procedure is used throughout the study.	If clinical symptoms suggest new bone lytic lesion.

* In case of serum troponin I increase, an ECG and ECHO will be performed as soon as possible, as well as further studies if judged necessary by clinical investigator. Any increase of troponin $I \ge ULN$ together with evidence of cardiac damage by ECG or ECHO/MUGA will be followed accordingly by a cardiologist and the patient will immediately and definitively discontinue study treatment.

treatment. PS-ECOG: Eastern Cooperative Oncology Group; BSA: body surface area; BP: blood pressure; WBC: white blood cells; CTCAE: National Cancer Institute Common Terminology Criteria for Adverse Events; AST: aspartate aminotransferase; ALT: alanine

TREATMENT	INVESTIGATIONS	TIME
-----------	----------------	------

aminotransferase; ULN: upper limit of normal; AP: alkaline phosphatase; CPK: creatine phosphokinase; CPK-MB: serum CPK isoenzymes (found in cardiac muscle); CT: computed tomography; LDH: lactate dehydrogenase; PT: prothrombin time, PTT: partial thromboplastin time, INR: international normalized ratio; ECG: electrocardiogram; LVEF: left ventricular ejection fraction; ECHO: echocardiogram; MUGA: multiple-gated acquisition scan; PK: pharmacokinetics; HCG: human chorionic gonadotropin; BM: bone marrow; FLC: free light chain; CR: complete response; MM: multiple myeloma; sCR, stringent complete response; D, day.

Note: One patient was still undergoing treatment on 19 May 2017. However, as the primary endpoint of the study (progression-free survival) was fulfilled, and this extended follow-up is focused only on survival, no information such as central laboratory data or images will be sent for independent review. Nevertheless, laboratory determinations or images will be done locally, if clinically indicated, in order to perform tumor assessment.

5.12 EVALUATION AT THE END OF TREATMENT

The end-of-treatment visit will be scheduled 30 days (\pm two days) after the administration of the last dose of the study therapy, unless another anticancer treatment is started before. In that case, the end-of-treatment visit should be performed immediately before the start of the new therapy (ideally the day before or the same day).

At the time of patient discontinuation (regardless of the reason), the same complete work-up done before study entry will be repeated.

- Physical examination, weight and height.
- ECOG performance status.
- Vital signs.
- Hematology and coagulation tests.
- Biochemistry (A and B).
- ECG: It should allow rhythm definition (at least 30 seconds of duration)
- LVEF assessment by ECHO or MUGA.
- Safety assessment (AEs).
- Serum protein: serum protein electrophoresis, immunoglobulins quantification, M-protein identification and quantification, and serum sFLC if indicated.
- Urine protein: Only if Bence-Jones proteinuria is present at entering the study.
- Serum β -2 microglobulin: only if the patient discontinues treatment without documented disease progression.
- Bone marrow (if clinically indicated).
- Radiological tumor assessment only in case of soft tissue plasmacytoma present at entering the study.
- Skeletal evaluation.
- Concomitant treatments.

Adverse events must be assessed for 30 days after the administration of the last study treatment. All SAEs occurring within 30 days of the last study drug administration will be reported. Beyond this period of time, only those suspected to be treatment-related SAEs will be reported (Section 9.2.2).

The Sponsor will evaluate any safety information that is spontaneously reported by an Investigator beyond the time frame specified in the protocol.

5.13 FOLLOW-UP AFTER END-OF-TREATMENT VISIT

Bone marrow evaluation, radiological tumor assessment and skeletal evaluation will be performed only on pre-treatment and treatment evaluations. These evaluations will not be performed after the end of treatment.

Patients who discontinued treatment without progression will be followed every four weeks until disease progression or other antitumor therapy, whichever occurs first. After progression, all patients will be followed every three months for survival until death, or until the date of study termination, whichever occurs first. Study termination date is defined as the date in which 80% of death events occurred, 24 months after the accrual of the last randomized patient, or IDMC recommendation (whichever occurs first).

Note: Two years after the last patient accrual, on 19 May 2017, the final OS analysis was done based on a total of 195 death events (i.e., 76.5% of the 255 randomized patients): 123 events in Arm A (plitidepsin plus dexamethasone) and 72 events in Arm B (dexamethasone). Then, the duration of this study is prolonged for six additional months, until 19 November 2017, in order to continue follow-up in the alive patients, and then to be able to reach the pre-specified total of 80% of death events (approximately 204 death events) or even more. If the required death events are not achieved on 19 November 2017, the study might be further extended by three to six months.

All AEs suspected to be related to study drug must be followed after the time of therapy discontinuation until the event or its sequel resolve or stabilize at a level acceptable to the Investigator and the clinical monitor or his/her designated representative. After treatment discontinuation, patients will be followed every four weeks until resolution of toxicities, if any.

Additional parameters and/or increased frequency of observations should be performed at the Investigator's discretion and according to the nature of the observed AEs. When available, autopsy data should be provided.

The follow-up visits will be performed by phone only if the patient is unable to go to the study center owing to the seriousness of his/her disease. This will only apply to patients who are followed up after discontinuing treatment due to disease progression.

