- 10. Serum protein electrophoresis, immunoglobulins quantification, M-protein identification and quantification, serum free light chains (sFLC) ratio and immunofixation will be performed in the Central Lab starting on Day 1 of Cycle 1 prior to treatment (complete protein panel). Patients with secretory MM will be followed with serum electrophoresis, immunoglobulins quantification and M protein quantification; patients with oligo or non-secretory MM will be followed with sFLC ratio, in case it has been abnormal at study entry; in case of M protein disappearance, immunofixation will be done to confirm CR, and if CR is confirmed, sFLC ratio will be performed, to determine stringent complete response (sCR). All protein assays will be done symmetrically every four weeks (i.e., Day 1 of each 4-week cycle, with a window of ± 2 days) in both treatment arms, irrespectively of treatment delays or omissions.
- 11. Urine immunoelectrophoresis and immunofixation in Central Lab: on Day 1 of Cycle 1, and afterwards, only if Bence-Jones proteinuria was present at entering the study. To be done symmetrically every 4 weeks (with a window of ± 2 days) in both treatment arms, irrespectively of treatment delays or omissions.
- 12. At screening (within 4 weeks prior to registration). In all patients, BM evaluation is mandatory at screening and while on treatment in case of CR (including flow cytometry or immunohistochemistry, to demonstrate the presence of clonal plasma cells, only in those patients with presumed CR). In patients with non-secretory MM, it must be repeated 6 weeks later to confirm response or as clinically indicated.
- 13. In case of measurable soft tissue plasmacytoma, involvement assessments should be done to evaluate all known affected sites every 8 weeks to confirm response or as clinically indicated. In truly non-secretory patients who discontinued treatment without progression, and only evaluable by measurable plasmacytomas, radiological assessments should continue every 8 weeks until progression.
- 14. Patients withdrawn with a drug-related AE should be followed until recovery. Beyond 30 days after the last administration of study drug, only those procedures that are relevant to any persisting toxicities need to be performed.
- 15. Only in patients who discontinued treatment without documented disease progression.

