By design, disease response will be assessed every four weeks symmetrically across treatment arms irrespectively of treatment delays or omissions. Disease assessments (e.g., serum or urine M protein, serum FLC) and evaluation of extent of disease will be done within two weeks before *randomization* and every four weeks thereafter in the absence of PD while on treatment. If disease progression has not occurred at treatment termination, then disease assessments should continue every four weeks until evidence of disease progression, start of subsequent anticancer treatment, or death, whichever occurs first.

PFS and objective tumor response will be assessed symmetrically across treatment arms every four weeks while on treatment, irrespectively of dose omissions or delays, according to IMWG criteria. Centralized laboratory reports and copies of CT scans, MRI (in case of soft tissue plasmacytoma) and any other documented means to evaluate tumor response or progression should be available for IRC review.

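### Protocol 5.13 and schedule footnote 16 bar imaging, marrow and skeletal evaluation after treatment without exception, which conflicts with footnote 13 and leaves some progressions with no scheduled assessment

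*Protocol*

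**What the plan says.** **The ban.** Section 5.13 opens: "Bone marrow evaluation, radiological tumor assessment and skeletal evaluation will be performed only on pre-treatment and treatment evaluations". It continues: "These evaluations will not be performed after the end of treatment". Footnote 16, attached to the follow-up column of the schedule of assessments, carries the same two sentences.

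**The rules that pull the other way.**
- Footnote 13 of the same schedule covers truly non-secretory patients who stopped treatment without progression. For those "only evaluable by measurable plasmacytomas, radiological assessments should continue every 8 weeks until progression".
- The skeletal row of the schedule ends with a mark followed by an entry for evaluation when clinically indicated. These fit the end-of-treatment and follow-up columns.
- The second paragraph of 5.13 states: "Patients who discontinued treatment without progression will be followed every four weeks until disease progression or other antitumor therapy, whichever occurs first".
- Section 8.1 states: "If disease progression has not occurred at treatment termination, then disease assessments should continue every four weeks until evidence of disease progression". SAP 6.1.2 carries the same four-weekly rule.

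**What continues off treatment.** Central serum and urine protein tests are marked in the follow-up column with footnote 15: "Only in patients who discontinued treatment without documented disease progression".

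**The concern.** PFS by IRC is the primary endpoint, and Appendix 5 defines progression by several components. New or growing bone lesions, new or growing plasmacytomas and a rise in marrow plasma cells each count. None of these can be read from a serum or urine protein test. A patient who stops treatment before progression stays at risk for the primary endpoint, so the assessment rule after treatment matters as much as the rule during it.

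A site that reads 5.13 or footnote 16 would do no imaging. A site that reads footnote 13 would scan a plasmacytoma-only patient every eight weeks. Both comply with part of the protocol, and the progression date that reaches the IRC depends on which part was read.

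**Working it through.** The contradiction rests on text, so the passages come first. A rough count follows.

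**1. Is there an exception that reconciles them?** The only limiting sentence near the ban says that a rule applies to patients who stopped because of progression. In both 5.13 and footnote 16 it directly follows the sentence on telephone visits and qualifies those visits. Nothing limits the ban itself. Footnote 13 and footnote 16 therefore conflict inside the schedule, as well as between the schedule and 5.13.

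**2. When does the gap begin?** Section 5.12 puts the end-of-treatment visit 30 days (± two days) after the last dose. It includes skeletal evaluation, imaging where a plasmacytoma was present at entry, and marrow if clinically indicated. Section 5.1 counts those 30 days as treatment, so the gap starts after that visit.

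**3. Which components of progression are lost under the ban?**
- Serum or urine protein: still assessed every four weeks (footnote 15).
- Death: still an event under 8.1.
- Plasmacytoma, bone lesion, marrow: no scheduled assessment.
- Calcium: the schedule marks no Biochemistry A in follow-up, so it is not a scheduled substitute.

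**4. Would the SAP's sensitivity analyses show it?** The three imputation analyses and the interval-censoring analysis (SAP 6.1.2 and 6.2.3) work on assessment dates or missed assessments. A patient with protein results but no skeletal evaluation looks fully assessed, so a skeletal-only progression would not be exposed.

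**5. How many patients?** The documents give no rates. For context, the plan's own event target reproduces approximately. With HR 0.625, 1-sided 2.5%, 90% power and 2:1 allocation, Schoenfeld's formula gives

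d = (1.960 + 1.282)² / [(2/3)(1/3)(ln 0.625)²] = 10.507 / (0.2222 × 0.2209) ≈ 214.05, rounded up to 215,

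against the stated 210. At 210 events power is Φ(√(210 × 0.04909) − 1.960) = 89.4%.

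Now assume that 5% to 20% of the 250 patients stop without progression, and that 30% of these progress only in bone, soft tissue or marrow:
- Low: 250 × 0.05 × 0.30 = 3.75, about 4 patients (4/210 = 1.9% of events).
- High: 250 × 0.20 × 0.30 = 15 patients (15/210 = 7.1% of events).

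If each of these were an event that was lost and not replaced, 206 events would give 88.9% power and 195 would give Φ(√(195 × 0.04909) − 1.960) = 87.2%. In practice the analysis waits for at least 210 events, so the more likely effect is late or missed dates rather than lost power. These figures bear on information only. Bias cannot be sized without rates by arm.

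**The case against.** **Much can be read together.** Section 8.1 names disease assessments, with protein tests as its examples, separately from evaluation of extent of disease. Only disease assessments are said to continue every four weeks off treatment. For a patient measurable by protein, the ban and 8.1 are compatible. This stands. The conflict with follow-up to progression is therefore confined to patients not evaluable by protein.

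**Little routine surveillance is lost.** Even on treatment, skeletal evaluation is triggered by symptoms and imaging is done only where there is a plasmacytoma. This also stands. What goes is symptom-triggered and plasmacytoma-specific testing.

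**The schedule table is unclear.** It did not survive text extraction intact. The skeletal entry fits the follow-up column, but the marrow entry cannot be placed with confidence, and the point does not rest on it. Footnote 13 is clear on its own.

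**There is a partial safeguard.** SAP 8.3 analyses time to first subsequent therapy or death regardless of how progression was detected. It is supportive and does not repair the primary endpoint.

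**Stronger readings that the documents do not support.**
- A reader might infer that plasmacytoma-only patients have no progression assessment at all after treatment. Footnote 13 orders radiology for exactly these patients, inclusion criterion 7 lets plasmacytomas be determined by clinical examination, and death counts. The inference holds only if the general ban overrides the specific footnote, and no order of precedence is given.
- A reader might infer that the gap favours Arm A, because more patients may stop for toxicity there. That is plausible, but the documents give no discontinuation rates by arm.
- A reader might infer that barred scans count as missing follow-ups, so that the rule on more than one missing follow-up censors later events. The documents do not say whether a scan that the protocol forbids is missing.

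**Conclusion.** The protocol contradicts itself on a rule that feeds the primary endpoint. Section 5.13 and footnote 16 cannot both be obeyed with footnote 13, and they do not fit the follow-up entry that appears in the skeletal row. For patients not evaluable by protein, they also clash with the requirement to follow unprogressed patients to progression.

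If the ban was followed, progression shown only by plasmacytoma, bone lesion or marrow after the end-of-treatment visit may be late or absent in IRC PFS. Protein progression and death are still captured. The effect on the hazard ratio is likely small. That is a judgement based on the small share of events involved under the assumed rates, since neither the number affected nor any imbalance between arms is documented. The textual conflict depends on none of these assumptions.

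**What to change.** Limit the ban in 5.13 and footnote 16 to patients who stopped because of progression. For patients who stopped without progression, keep the assessments already foreseen, namely footnote 13's 8-weekly radiology and the entries for evaluation when clinically indicated, until progression or new therapy. Clarify the follow-up column to match. The cost is a few lines of protocol wording and no assessment beyond those the schedule already contains.

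Rewording cannot recover scans that were not done. The notes to the schedule and to Table 4 in 5.11 record that the primary endpoint was fulfilled and that images are no longer sent for independent review. The study report should therefore also state which rule sites followed. It should list, by arm, the patients who stopped without progression and had no later imaging, with their type of measurable disease and their PFS status and date. This needs one listing from existing data, and it would replace the assumed rates above with observed counts.
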